### **Daily Bowel Habits:**

Baseline daily stool consistency will be assessed for one week prior to device placement (using 7-point BSFS). Daily stool consistency will again be assessed for one week after the 4th device placement. We will then compare the 4-week change-from baseline in stool consistency between patients who received the PENFS therapy compared to sham therapy.

### **IBS Quality of Life (IBS-QOL)**

Health-related QOL will be assessed using the IBS-QOL, a validated IBS specific survey containing questions that assess disease-specific QOL over the past 30-days, with lower scores indicative of poorer health-related QOL (score range 1-100). Patients will complete the IBS-QOL at baseline/visit 1 (in person) and at extended follow-up (week 8) using an online survey questionnaire.

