***Secondary Aims:***

To compare the efficacy of PENFS therapy versus sham therapy on:

1. the change in mean IBS-SSS at week 8 compared to baseline.
2. the proportion of adult patients with IBS who experience at least a 50-point reduction on the IBS-SSS after 4 weeks of treatment and at the extended follow up period at week 8. These patients are considered clinical responders.
3. the proportion of adult patients with IBS who experience an improvement of  $\geq 30\%$  from baseline in weekly average of the daily worst abdominal pain scores after 4 weeks of treatment. These participants are considered a responder.
4. the change in mean weekly average of the daily worst abdominal pain scores after 4 weeks compared to baseline in adult patients with IBS.
5. the change in average weekly abdominal pain symptoms after 4 weeks of treatment and at extended follow-up (8 weeks) compared to baseline, assessed through the PROMIS Gastrointestinal Belly Pain Scale.
6. the change in average daily stool consistency after 4 weeks of treatment compared to baseline, assessed using the Bristol Stool Form Scale (BSFS).
7. the change in average weekly bowel habits after 4 weeks of treatment and at extended follow-up (8 weeks) compared to baseline, assessed through the PROMIS Gastrointestinal Constipation Scale and Gastrointestinal Diarrhea Scale.
8. the change in average weekly bloating symptoms after 4 weeks of treatment and at extended follow-up (8 weeks) compared to baseline, assessed through the PROMIS Gastrointestinal Gas and Bloating Scale.
9. the change in IBS-QOL in adult patients with IBS after 4 weeks of treatment and at extended follow-up (8 weeks) compared to baseline.
10. the change in resting cardio-autonomic tone, i.e. HRV, over 4 weeks of treatment compared to baseline.
11. the safety and tolerability of PENFS therapy versus sham therapy in adult patients with IBS.

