##### **6. Technology**

The IB-Stim/PENFS device consists of a battery activated generator and wire harness that connects to the generator. Four leads are also attached to the generator, each with a sterile 2 mm, titanium needle. Prior to device placement, the patient's ear is cleaned with alcohol wipes and the ear is trans-illuminated to identify neurovascular bundles that are avoided during needle placement. The generator is attached with adhesive to the skin behind the patient's ear, just above the mastoid process. Each of the 2 mm needles are inserted into the dorsal and ventral aspects of the ear, within 1-1.5 mm of the visualized vascular branches to create a field effect. The PENFS device settings are standardized and deliver 3.2 volts with alternating frequencies (1 ms pulses of 1 Hz and 10 Hz) every 2 s. This stimulation targets central pain pathways through branches of cranial nerves V, VII, IX, and X, which innervate the external ear. The PENFS device generator has a battery life of 5 days and delivers stimulations in 2-hour cycles. Patients remove the device at home on day 6 of treatment. Original protocol from Kovacic et al.

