### ***Assessments and Questionnaires:***

Administration of questionnaires throughout the study is shown in Table 1 and Figure 2.

Patients will provide telephone consent for enrollment into the study. During the this phone call, the investigator will obtain the participant's medical and medication history to check eligibility. After enrollment, patients will complete an online daily questionnaire to assess daily stool consistency (7-point Bristol Stool Form Scale [BSFS]) and a daily question pertaining to daily worst abdominal pain (measured using an 11-point scale) that will be delivered by the smart watch, for one week prior to device placement. If patients do not elect to use the SmartWatch, then they will complete the daily question pertaining to daily worst abdominal pain via an online questionnaire. The questionnaires will provide a baseline for daily worst abdominal pain and stool consistency. In order to be enrolled into the study, patients must have an average daily worst abdominal pain score between 4 and 8, have a minimum of 2 days per week of abdominal pain, and have completed at least 4 out of 7 of the daily worst abdominal pain questionnaires.

If enrollment criteria are met, patients will then present to the UCLA G. Oppenheimer Center for Neurobiology of Stress and Resilience one week after enrollment for their first visit, where they will get a physical examination, complete additional questionnaires, undergo a measurement of HRV, and have the initial PENFS device placed by a trained health care professional (LC, AL, EL). After initial device placement, patients will be instructed to return to UCLA every 7 days (leeway of +/- 2 days in each direction will be allowed) for a total of 4 visits for device replacement and completion of additional questionnaires. Four different devices will be placed in total (at the start of weeks 1, 2, 3, and 4).

Although the IB-Stim device is currently FDA approved for use for 3 consecutive weeks, children in the original study by Kovacic et al actually received 4 consecutive weeks of device treatment. The authors chose to analyze the data after 3 consecutive weeks as children did not return to the clinic after the 4th week of treatment. However, we will analyze IBS symptom severity, abdominal pain, bloating, and bowel habits after the completion of the 4th week of treatment. Again, actual stimulation time is 5 days per week with 2

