### Statistical Analysis

Fisher tests will be used to evaluate for differences in categorical variables and a 2-tailed t-test and Mann-Whitney-U (MWU) test will be used for assessing differences between normally distributed continuous data and non-normally distributed continuous data, respectively. The data will be analyzed using R statistical analysis software.

The change in IBS-SSS score from baseline will be computed using a generalized linear mixed effect model. We will include treatment, time, and treatment x time as covariates. Tukey's honestly significant difference will be used for multiple comparisons. Data will be analyzed based on a modified intention-to-treat approach. Specifically, patients with less than one full week of data will be excluded from the study.

For all the secondary Aims, a simple 2-sample analysis (T-, MWU or Fisher's) test for changes in outcomes will be performed.

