### **UCLA budget and costs**

The remaining costs of the personnel, equipment, patient stipends, and statistical support will be provided by the PI and Division of Digestive Diseases. This will include a research coordinator to assist with patient recruitment and coordination for this project. Equipment to measure HRV is also available through the UCLA G. Oppenheimer Center for Neurobiology of Stress and Resilience at no additional cost. Budget is outlined in Table 2.

[figure not shown]
**Human Subject Stipends.** Patient stipend payments include parking. Parking rate at UCLA is \$13 per in-person visit, each subject will have 4 in-person visits (\$52/subject total). Patients will be paid stipends of \$25 per set of questionnaires and we expect each subject to complete 7 sets of questionnaires not including the daily abdominal pain questionnaire (baseline, 4 visits, week 4 follow-up, week 8 follow-up). This equates to \$175/subject, making the total payment per subject to be \$227 with an additional driving compensation if applicable.

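### The IBS-QOL section leaves out the week-4 assessment that secondary aim 9 and Table 1 both call for, and the week-8 score cannot stand in for it

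*Combined protocol and SAP*

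**What the plan says.** Three places in the combined protocol and SAP set the timing of the IBS-QOL.

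- **Section 7, IBS Quality of Life (IBS-QOL):** "Patients will complete the IBS-QOL at baseline/visit 1 (in person) and at extended follow-up (week 8) using an online survey questionnaire". Week 4 is not mentioned.
- **Secondary Aims, item 9:** "the change in IBS-QOL in adult patients with IBS after 4 weeks of treatment and at extended follow-up (8 weeks) compared to baseline".
- **Table 1, IBS-QOL row:** marked at Visit 1, End of Week 4 and 8-week follow up.

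The opening of Assessments and Questionnaires refers the reader to Table 1 and Figure 2 for when questionnaires are given, and the end of the HRV section does so again. Figure 2 is not available in the text reviewed, so it is not counted for either side.

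**The concern.** The section that defines the instrument and the aim that uses it disagree on when it is measured. The section reads as complete: it gives a time and a mode for each administration. The neighbouring IBS-SSS and PROMIS sections do name the week-4 online survey. Someone building the week-4 survey from the instrument sections could therefore leave the IBS-QOL out in good faith.

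The analysis needs a value at each time the aim names: "For all the secondary Aims, a simple 2-sample analysis (T-, MWU or Fisher's) test for changes in outcomes will be performed". Without a week-4 score, the first of aim 9's two comparisons cannot be done for any participant, and a missed questionnaire cannot be recovered later. What remains is a week-8 score whose recall period may barely touch treatment. The check below measures how far week 8 could replace week 4.

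**Working it through.** The plan gives no power or precision figure for the IBS-QOL, so there is none to reproduce. The check compares the sources and then counts days.

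**Step 1: the sources side by side**

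| Source | Visit 1 | End of week 4 | Week 8 |
|---|---|---|---|
| IBS-QOL section | yes | no | yes |
| Secondary aim 9 | yes (as baseline) | yes | yes |
| Table 1 | yes | yes | yes |

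Text and table also differ for two other instruments. The VSI text puts the follow-up at 8 weeks, while Table 1 puts it at End of Week 4. The IBS-SSS text gives week 1, after week 4 and week 8, while Table 1 adds Baseline and the ends of weeks 1, 2 and 3. The IBS-QOL is thus one of several mismatches, and no sentence says which source governs.

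**Step 2: inputs for the recall window**

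- Recall of 30 days, from the IBS-QOL section: "questions that assess disease-specific QOL over the past 30-days".
- Placements, from Assessments and Questionnaires: "Four different devices will be placed in total (at the start of weeks 1, 2, 3, and 4". With day 0 as the first placement, these are nominal days 0, 7, 14 and 21.
- Five stimulation days per device, then two off. Section 6, Technology, gives a 5-day battery life and says "Patients remove the device at home on day 6 of treatment".
- Visit leeway, from Assessments and Questionnaires: return visits are "every 7 days (leeway of +/- 2 days in each direction will be allowed".
- Treatment period: first placement to 7 days after the last placement, nominally days 0 to 28.

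For an assessment on day T the recall window is [T − 30, T). Its overlap with an interval [c, d) is max(0, min(T, d) − max(T − 30, c)). Two measures are kept apart: stimulation days (5 after each placement) and treatment-period days.

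**Step 3: week 8 on day 56, recall window [26, 56)**

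- *Nominal schedule.* The last stimulation is [21, 26), so overlap is 0. The treatment period ends on day 28: 28 − 26 = 2 of 30 days (6.7%).
- *Each later placement 2 days late against the original schedule.* The last placement is day 23 and stimulation is [23, 28): 28 − 26 = 2 days. The period ends on day 30: 30 − 26 = 4 of 30 (13.3%).
- *Delays accumulating to 6 days, week 8 fixed at day 56.* The last placement is day 27 and stimulation is [27, 32): 5 days. The period ends on day 34: 34 − 26 = 8 of 30 (26.7%).
- *Visits accumulating 6 days early.* The last placement is day 15 and the period ends on day 22: 0 on both measures.

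**Step 4: week 8 read as 8 weeks after treatment ends**

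T = 28 + 56 = 84, recall window [54, 84). Overlap is 0 on both measures under every visit pattern above.

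**Step 5: week 4 on day 28, nominal schedule, recall window [−2, 28)**

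Stimulation days: 4 × 5 = 20, all inside the window. Treatment-period days: 28 of 30 (93.3%).

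**Like for like on the nominal schedule:** 0 against 20 stimulation days, and 2 against 28 treatment-period days. The least off-treatment week-8 case leaves (30 − 8)/30 = 73.3% of the recall outside the treatment period.

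**The case against.** The strongest reply is that the documents name Table 1 as the schedule, and Table 1 has week 4. Aim 9 agrees with it. Two of three sources therefore have the assessment, and a coordinator working from the table would collect it. This stands: loss of the week-4 score is conditional on the IBS-QOL section being followed. It does not remove the contradiction, because the plan has no rule of precedence and the text departs from the table elsewhere.

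A second reply is that a reader might infer that the trial will have no quality-of-life result from the treatment period, or that week 4 was dropped on purpose. The documents support neither. Aim 9 and Table 1 show that week 4 was intended, and the other mismatches look like incomplete editing.

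A third is that a reader might infer that hypothesis 6 becomes untestable. It does not. Hypothesis 6 names no time point, so a randomised comparison at week 8 still bears on it. Benefit after treatment is also something the trial wants to measure: hypotheses 1, 3 and 4 all name the extended follow-up. A recall window lying mostly after treatment is what a follow-up score should have. It is a problem only if that score has to serve for the 4-week comparison as well.

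Finally, the scale is limited. This is one of eleven secondary aims in a pilot study, and neither the primary endpoint nor the sample size depends on it.

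**Conclusion.** The contradiction is real and should be corrected. If the IBS-QOL section is followed, the week-4 half of aim 9 cannot be analysed, while the week-8 half survives. The week-8 score is no substitute: its recall covers between 0 and 8 of 30 treatment-period days, and 2 on the nominal schedule, against 28 of 30 at week 4.

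Two assumptions carry the day counts. The first is the origin of week 8. Day 56 from first placement is the working reading, but the IBS-SSS and PROMIS sections also speak of 8 weeks after treatment, which would bring the overlap to zero. The second is whether the 2-day leeway accumulates from visit to visit; the figure of 8 days needs it to do so with week 8 held at day 56. At least 73% of the recall is off treatment under every reading examined, so the conclusion does not turn on either assumption. The week-4 figures are for the nominal schedule.

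This is an inconsistency to repair at a secondary endpoint. It is not evidence of a decision to drop the assessment or of data already lost.

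**What to change.** Amend the scheduling sentence in the IBS-QOL section so that the questionnaire is completed in person at baseline/visit 1, and by online survey both at the end of week 4 and at the week-8 follow-up. That matches aim 9 and Table 1, neither of which needs to change for the IBS-QOL.

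The cost is one sentence. The IBS-SSS and PROMIS sections already send an online survey at that time, and the stipend budget counts seven questionnaire sets per participant: "baseline, 4 visits, week 4 follow-up, week 8 follow-up". No extra visit or payment follows; the IBS-QOL only has to be in the week-4 set.

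An optional addition is to label the week-4 change as the treatment-period comparison and the week-8 change as durability. This would help interpretation, but removing the contradiction does not require it.

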### **Hospital Anxiety and Depression Scale (HADS) and Visceral Sensitivity Index (VSI)**

Psychological symptoms will be evaluated using the HAD scale for depression and anxiety (each with a score range from 0-21). GI symptom related anxiety will be measured using the VSI. This questionnaire contains statements regarding how individuals may potentially react with anxiety, worry, or fear to different GI symptoms. Patients respond with how strongly they agree or disagree with each statement (0-strongly disagree to 5-strongly agree), with total scores ranging from 0-90. Patients will complete both the HADS and VSI at baseline/visit 1 and will also complete the VSI after 8 weeks of extended follow-up using online survey questionnaires.

### **Heart Rate Variability (HRV)**

HRV will be assessed at baseline/visit 1 and at the end of weeks 1, 2, and 3 (visits 2, 3, and 4 respectively) of treatment, with the goal to determine if HRV (cardio-autonomic tone) changes over 4 weeks of PENFS treatment vs. sham treatment and if HRV predicts response to PENFS. The previous protocols used for HRV analysis have previously been published by members of our research group and are summarized below. HRV will be recorded for 5-minute intervals using a 2-lead electrocardiogram (ECG) attached to patients' upper chest. ECG data will be collected using the BioPac recording system (MP100A-CE; BioPac Inc., Santa Barbara, CA, USA) and will be manually screened for artifacts. The AcqKnowledge peak detection algorithm (V3.8.2; BioPac, Inc.) will be used to determine intervals between adjacent QRS complexes. The interbeat (R-R) interval data will be used for HRV analysis (Kubios HRV 2.0, Biosignal Analysis and Medical Imaging Group, Dept. of Physics, University of Kuopio, Finland). Autoregression (AR) frequency analysis and Fast Fourier transform (FFT) analysis were performed on one continuous 2-minute segment (epoch) of data to avoid inclusion of artifacts, which can distort HRV data. The AR and FFT analyses should yield measures of HF power in normalized power based on a frequency band of 0.15-0.4 Hz and the LF/HF ratio with LF power defined as the interval between 0.04 and 0.15 Hz. A model order of 16 will be used in the AR analysis with no spectral factorization. FFT analysis will use Welch's periodogram method with a window width of 256 s and window overlap of 50%.

The timing of device placements, questionnaires, and HRV assessment is further outlined in Table 1 and Figure 2.

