#### **Smart Watch Technology**

In collaboration with a UCLA research group led by [name] (IRB IRB#16-000166) participants will have the option to be given a SmartWatch system. This system includes ambient location and activity sensors, wireless data transmission, specialized software application, and analytic engine for functional and performance measurement. This platform allows for the detection and classification of patient motion and position with an accuracy of over 85%. In this study, we want to be able to monitor subject activity and abdominal pain in real time. Data will also be collected to measure HRV. With collected of HRV data in a standard manner with each in-person visit, we will be able to validate SmartWatch measurements of HRV.

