**Table 1: Timing of PENFS vs Sham Interventions, Questionnaires, and HRV**

	Daily	Baseline	Screening (Visit 1)	End of Week 1 (Visit 2)	End of Week 2 (Visit 3)	End of Week 3 (Visit 4)	End of Week 4	8-week follow up
Consent + Enrollment		X						
History		X						
Daily Worst Abdominal Pain (via Smart Watch)	X	X (daily for 1 week)		X (daily during week 1)	X (daily during week 2)	X (daily during week 3)	X (daily during week 4)	
Daily BSFS		X (daily for 1 week)					X (daily during week 4)	
Physical			X					
PENFS vs Sham Device Placement			X	X	X	X		
Rome IV		X						
Bowel Symptom Questionnaire (BSQ)			X					
UCLA CNSR Participant Demographics			X					
IBS-SSS		X	X	X	X	X	X	X
PROMIS Questionnaires			X	X	X	X	X	X
IBS-QOL			X				X	X
HAD			X					
VSI			X				X	
Heart Rate Variability			X	X	X	X		

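### Clinic HRV stops after three of four devices but is described as a 4-week change, and the 256 s Welch window cannot be applied to the 120 s epoch

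*Combined protocol and SAP*

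**What the plan says.** **Timing.** Secondary aim 10 compares the arms on "the change in resting cardio-autonomic tone, i.e. HRV, over 4 weeks of treatment compared to baseline". The HRV section gives its goal as whether HRV "changes over 4 weeks of PENFS treatment vs. sham treatment", and also whether it predicts response. The schedule in the same sentence is that "HRV will be assessed at baseline/visit 1 and at the end of weeks 1, 2, and 3", that is, visits 1 to 4. The HRV row of "Table 1: Timing of PENFS vs Sham Interventions, Questionnaires, and HRV" matches: it is marked at visits 1 to 4 and blank at the end of week 4 and at the 8-week follow-up. Under Assessments and Questionnaires, "Four different devices will be placed in total (at the start of weeks 1, 2, 3, and 4"), so the fourth goes on at visit 4, and "actual stimulation time is 5 days per week". The budget section confirms that "each subject will have 4 in-person visits". Under Smart Watch Technology, "participants will have the option to be given a SmartWatch system"; the watch also collects HRV, which is to be validated against the recordings made at the visits. The Statistical Analysis section assigns every secondary aim a simple two-sample test of change and names no time point for HRV.

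**Spectral analysis.** The HRV section records 5 minutes of ECG and analyses a single uninterrupted 2-minute stretch by AR and by FFT, to obtain HF power and the LF/HF ratio. The FFT is to use Welch's method with windows 256 s long, overlapping by half. The section says that it summarises protocols the group has already published.

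**A minor point of the same kind.** The IBS-QOL section lists visit 1 and week 8 only, whereas secondary aim 9 and Table 1 also include week 4.

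**The concern.** Elsewhere in the secondary aims, 4 weeks means the end of week 4, so a reader will take aim 10 the same way. The clinic data cannot support that reading, because nothing is recorded after the fourth device has been worn. A mechanistic result at three weeks could then be set beside symptom results at four weeks as if they shared a time point. A two-sample test also needs one change value per participant, and with three post-baseline visits available the plan does not say which supplies it.

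The window problem is different in kind: it is a stated setting that cannot be carried out. If it is left as it is, the FFT values of HF power and LF/HF will depend on what the software does with a window longer than the data, which the plan does not describe.

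**Working it through.** **1. Exposure at the last clinic recording.** Inputs: 4 devices, placed at visits 1 to 4; 5 stimulation days per device; last HRV at visit 4 (Assessments and Questionnaires; HRV section; Table 1).

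- Devices completed by visit 4: 3 of 4.
- Stimulation days: 3 × 5 = 15 of 4 × 5 = 20, or 75%.
- Clinic HRV recordings after the fourth device: 0.

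The 15 days are nominal, since each visit may move by 2 days either way. That leeway does not add a recording after the fourth device.

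**2. Contrasts left open.** Post-baseline visits: 3. Measures: 2 (HF power, LF/HF). Candidates: 3 × 2 = 6, treating AR and FFT as two estimates of the same quantity; counted separately, 6 × 2 = 12. Naming visit 4 and one method leaves 1 × 2 = 2.

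**3. Welch windows.** With data length L and window W at 50% overlap, the number of full windows is 1 + floor((L − W)/(W/2)) if L ≥ W, and 0 otherwise. The plan's own setting comes first.

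| L (s) | W (s) | Full windows |
|---|---|---|
| 120 | 256 | 0 (256/120 = 2.13) |
| 300 | 256 | 1 |
| 120 | 120 | 1 |
| 120 | 80 | 2 |
| 120 | 60 | 3 |

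Two half-overlapping windows of 256 s need 256 + 128 = 384 s, which is longer than the 300 s recording. The stated overlap could therefore not operate even if the whole recording were analysed. The longest window that gives two half-overlapping windows in 120 s is 120/1.5 = 80 s.

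**4. Is 256 s a slip for 256 samples?** This is an assumption, and the documents give no interpolation rate. 256 samples last 128 s at 2 Hz (does not fit), 64 s at 4 Hz (2 windows) and 32 s at 8 Hz (6 windows). Two windows fit only at 256/80 = 3.2 Hz or faster. The documents cannot settle it.

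**5. What a shorter window costs in the LF band.** Without zero-padding, frequency points lie at k/W; count those from 0.04 to below 0.15 Hz.

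| W (s) | k | LF points | Cycles at 0.04 Hz |
|---|---|---|---|
| 120 | 5–17 | 13 | 4.8 |
| 80 | 4–11 | 8 | 3.2 |
| 60 | 3–8 | 6 | 2.4 |

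These counts describe the candidate replacements. They do not measure an error in the planned result.

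**The case against.** The schedule is stated openly, in the same sentence as the goal and again in Table 1. Aim 10 says over 4 weeks where most of the other week-4 aims say after, which could mean serial measurement during a 4-week course. Hypothesis 5 gives no HRV time point at all. That the result would be reported as a 4-week effect is an inference about reporting. These points are fair, but they do not remove the gap: even on the serial reading the last week of treatment goes unobserved, and the planned test still has no named end value.

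On the window, the text condenses earlier published methods, and the epoch sentence is in the past tense, so 256 s may be carried over or a unit slip. That may explain the figure, but the window sentence says what this trial will use, and the two settings conflict. AR has no Welch window and yields both measures, which limits the harm; it does not make AR the planned choice. The 80 s limit applies only if averaging over at least two windows is wanted. A single 120 s window would also be coherent, but without overlap.

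The strongest remaining argument is about weight: this is one of eleven secondary aims in a pilot, and no scheduled data are lost. The IBS-QOL point is purely editorial, since Assessments and Questionnaires already points to Table 1 for the schedule.

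**Conclusion.** The concern holds in both main parts. Clinic HRV can support a change from baseline to the end of week 3, after 3 of 4 devices and nominally 15 of 20 stimulation days. It cannot support a 4-week change, and optional, unvalidated SmartWatch HRV does not supply a week-4 value for every participant. The Welch setting cannot be executed as written: 0 full windows fit in the 120 s epoch.

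The window result rests only on the epoch, window and overlap given in the HRV section. Whether 256 s is a unit slip stays open. The size of any distortion in the FFT values is not quantified, because it depends on software behaviour that the plan does not state. The scope is secondary aim 10 and the related goal of predicting response from HRV; the primary IBS-SSS endpoint is not affected. The correction should be made, because it changes what aim 10 can conclude and costs little.

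**What to change.** 1. Restate secondary aim 10 and the goal in the HRV section as the change from visit 1 to visit 4, after three weeks of treatment. In Statistical Analysis, name visit 4 as the end value for the two-sample test. Label any week-4 SmartWatch HRV as exploratory.
2. Before HRV is analysed, confirm the intended Welch setting, including whether 256 s was meant as samples. Replace it with a window that fits the 120 s epoch, at most 80 s if two half-overlapping windows are wanted. Name either AR or the corrected FFT as the tested estimate.
3. As a minor edit, add week 4 to the IBS-QOL section to match aim 9 and Table 1.

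**Cost.** These are text changes only: no added visit, recording or questionnaire, and the 2-minute epoch chosen to avoid artifacts is kept. The HRV claim becomes a three-week claim, and visits 2 and 3 become supporting data for the tested contrast. If FFT is the tested method, a shorter window coarsens the LF band (8 points at 80 s or 6 at 60 s, against 13 for one 120 s window) in exchange for averaging 2 or 3 windows. AR avoids that loss, but like any method on 120 s of data it sees only 0.04 × 120 = 4.8 cycles at the lower LF limit.
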